4.2.5 Day of SRS

- 4.2.5.1** Documentation of corticosteroid use/no dexamethasone (or any other corticosteroid with the purpose of treating cerebral edema) use.

4.2.5.2 Continued fingerstick glucose draws by patient once a day (in the morning before breakfast [fasting]) for at least 1 week after SRS. Please see section 5.4.2 for further details.

4.2.6 1 week after SRS (± 3 days)

4.2.6.1 Review the patient's blood glucose and medication administration logs.

4.2.6.2 CBC with differential and CMP including LFTs.

4.2.6.3 Fingerstick Glucose draw by nurse/research team member.

4.2.6.4 Adverse event evaluation. If no "*concerning toxicity*" or "*serious toxicity*" (see section 5.3.2), then patient will be instructed to discontinue blood glucose monitoring.

4.2.6.4.1 If the patient does have a "*concerning toxicity*" or "*serious toxicity*" they must discontinue their investigational medication (see section 5.3.2) and thus can also discontinue with fingerstick glucose draws.

4.2.6.5 Documentation of corticosteroid use (record the date of initiation, dose and reason for initiation of any new corticosteroid, especially dexamethasone).

4.2.7 1 month after SRS (- 5 or + 10 days)

4.2.7.1 Discontinue investigational medication (last dose is taken the evening of obtaining the follow-up MRI). Have patient return all remaining (untaken) investigational medication tablets.

4.2.7.2 Follow-up brain MRI with and without contrast. T1-weighted, T2, and/or FLAIR MRI of the brain (maximum slice thickness 5mm). FLAIR imaging is preferred.

4.2.7.2.1 T1 post gadolinium sequence will be imported into the Eclipse treatment planning system and the radiation oncologist (who will be blinded to the patient's investigational medication) will contour the enhancing tumor that received the prescribed dose of SRS.

4.2.7.2.2 FLAIR sequence will be imported into the Eclipse treatment planning system. FLAIR volume will be automatically calculated using "Region Growing" on Eclipse (Appendix I). The automated contours will be verified and modified as needed by the radiation oncologist who will be blinded to the patient's investigational medication.

4.2.7.3 Follow-up history and physical with neurologic examination and corticosteroid use documentation (record the date of initiation, dose and reason for initiation of any new corticosteroid, especially dexamethasone). A last fingerstick glucose draw will be done by the nurse/research team member.

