8.2 Non-Permitted Supportive Therapy

- 8.2.1** Corticosteroids: Dexamethasone (or any other corticosteroid whose purpose is to treat cerebral edema) should only be administered if the patient is clinically symptomatic, has imaging demonstrating increasing cerebral edema, and is deemed by the treating physician to require dexamethasone (or another corticosteroid). If administered between SRS and the one month follow-up MRI, these patients will be recorded as a treatment failure (primary endpoint). If initiated prior to SRS, this is criteria for withdrawal from the protocol, these patients would be deemed inevaluable. If initiated after the one month follow-up MRI, the dose, value, and reason will be recorded. Low dose prednisone or other non-dexamethasone steroids are allowed as long as they are not administered with the intent of treating cerebral edema.

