9.0 STATISTICAL CONSIDERATIONS

9.1 Definition of primary outcome/endpoint

9.1.1 Pilot Portion: Occurrence of Dose Limiting Toxicities (DLTs) between the time of glyburide initiation and the time of the one month follow-up MRI.

9.1.2 Randomized Portion:

Each eligible patient will be evaluated for treatment outcome as success or failure, as defined later in this section. Each patient's treatment outcome will be associated with randomized regimen regardless of the treatment the patient actually receives. A treatment failure will be considered to have occurred if edema increases sufficiently to require the initiation of dexamethasone (or any corticosteroid administration with the purpose of treating cerebral edema) between the time of SRS* and the time of the one month follow-up MRI, or the patient dies in that same interval from a cause considered probably or likely related to Glyburide. Otherwise, the patient will be considered to have experienced treatment success.

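### The failure window closes at the one-month MRI, the first scheduled scan that can justify an edema steroid, so a steroid started because of that scan is probably scored a treatment success

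*Combined protocol and SAP*

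**What the plan says.** Section 8.2.1 sets joint conditions for an edema steroid: it "should only be administered if the patient is clinically symptomatic, has imaging demonstrating increasing cerebral edema", and the treating physician must also judge it necessary. It then scores use by timing. Before the scan: "If administered between SRS and the one month follow-up MRI, these patients will be recorded as a treatment failure (primary endpoint". After the scan: "If initiated after the one month follow-up MRI, the dose, value, and reason will be recorded".

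Section 9.1.2 defines failure as an edema increase large enough to need a steroid "between the time of SRS* and the time of the one month follow-up MRI, or the patient dies in that same interval" of a cause probably or likely related to glyburide. For everyone else: "Otherwise, the patient will be considered to have experienced treatment success". Section 9.3.2 compares these successes between the arms, and 9.5.2 powers that comparison.

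The visit schedule (4.2.5 to 4.2.7 and Appendix VIII, Randomized Portion) lists no brain MRI between SRS and the one-month scan. That scan has a visit window of 5 days early to 10 days late, and the last dose of study drug is taken that evening (4.2.7.1).

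Other sections define the endpoint differently. Section 8.4.6 names edema increase, as measured under 8.4.4 and 8.4.5 on the one-month MRI, as the primary endpoint, with no steroid requirement. Sections 2.1.2 and 2.3.2 name both edema increase and steroid start, joined by the word and.

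**The concern.** One scan does two jobs. It is the first planned image that can meet the 8.2.1 condition for a steroid, and it is the event that ends the period in which a steroid counts as failure. Take a patient who has symptoms at the one-month visit, is scanned, shows increasing edema and starts dexamethasone as a result. That start comes after the scan. Section 8.2.1 files it as information only, and the default clause of 9.1.2 makes the patient a success. Yet this is steroid-requiring edema arising after a full course of study drug, the outcome the treatment is meant to prevent.

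The closing date also moves with the scan. Two patients who start a steroid on the same study day can be scored oppositely if one has already been scanned and the other has not.

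At stake is the go/no-go decision in 9.3.2, which rests on 20 patients per arm. Moving true failures into the success column raises success in both arms and, if the share moved is similar in each, shrinks the difference the trial was sized to detect.

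**Working it through.** **Scoring, with the passages side by side**

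| Situation (symptomatic patient, edema increasing) | 8.2.1 | 9.1.2 |
|---|---|---|
| Unscheduled scan before the one-month MRI, steroid started before that MRI | failure | failure |
| First qualifying image is the one-month MRI, steroid started on a later day because of it | recorded only | success, on the more natural reading |
| Same, but steroid started on the day of the scan | wording about starts after the scan points to recorded only | unsettled: the window runs "between the time of SRS* and the time of the one month follow-up MRI" |
| Death in the window, probably or likely related to glyburide | not addressed | failure |

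Under 8.4.6, the patients in rows 2 and 3 would be endpoint events if their increase met 8.4.4 or 8.4.5, whatever the steroid date.

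**Closing date.** Appendix VIII puts the one-month visit at day 30. The window therefore closes between day 30 − 5 = 25 and day 30 + 10 = 40, depending on the scan.

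**The plan's own power figure.** Inputs from 9.3.2 and 9.5.2: 20 per arm, success 50% on placebo and 75% on glyburide, one-sided exact test, p ≤ 0.30. I took the exact test to be Fisher's. Every pair of success counts (x on glyburide, y on placebo, each 0 to 20) is enumerated:

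Power = Σ Bin(x; 20, p_G) · Bin(y; 20, p_P), summed over pairs with one-sided Fisher p ≤ 0.30.

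With p_P = 0.50 and p_G = 0.75 this gives 0.802, which reproduces the stated 0.80.

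**Effect of the scoring rule.** Assume that a share f of would-be failures in each arm is triggered by the one-month MRI and scored as success, and that the planned rates count these patients as failures. The documents give no value for f. Scored success is then

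- placebo: 0.50 + 0.50f
- glyburide: 0.75 + 0.25f
- difference: 0.25(1 − f)

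| f | Placebo | Glyburide | Difference | Power |
|---|---|---|---|---|
| 0 | 50% | 75% | 25 points | 0.802 |
| 0.1 | 55% | 77.5% | 22.5 points | 0.756 |
| 0.2 | 60% | 80% | 20 points | 0.704 |
| 0.4 | 70% | 85% | 15 points | 0.578 |
| 0.5 | 75% | 87.5% | 12.5 points | 0.503 |

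**If f differs by arm.** The scored difference is 0.50(1 − f_P) − 0.25(1 − f_G). With f_P = 0 and f_G = 0.5 it is 0.50 − 0.125 = 0.375, wider than planned. The narrowing therefore depends on the shares being similar.

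**The case against.** The strongest reply is that 9.1.2 is not the only definition. Section 8.4.6 would count a patient with a qualifying increase on the one-month MRI, so under that section many of these patients are not lost. This stands as a conflict to be reconciled, but it does not repair the rule: treatment success, the quantity tested in 9.3.2 and powered in 9.5.2, is defined only in 9.1.2.

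Second, the interval in 9.1.2 can be read as attaching to the edema increase and the need for treatment, not to the steroid start. An increase visible on the one-month scan arose before that scan. This reading is possible. The timing rule in 8.2.1 favors the other one, and a primary endpoint should not leave the choice open.

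Third, a reader might infer that hardly anyone can be scored a failure. The documents do not support that. Unscheduled imaging of a symptomatic patient is not forbidden, and a glyburide-related death also counts. The gap concerns patients whose first qualifying image is the scheduled scan.

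Fourth, f has no source, and 9.5.2 does not say whether the 50% placebo rate includes starts triggered by the MRI. This stands, and the power figures are conditional on both points. The scoring rule is also the same in both arms and the study is blinded, so the harm shown is possible loss of power. A reader might infer bias for or against glyburide; nothing in the documents establishes it.

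Finally, later starts are reported under secondary endpoint 2.4.2.1. They enter only the three-month count, mixed with about two months off drug, and do not drive the decision.

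**Conclusion.** The concern holds as a gap in the endpoint definition. Under 8.2.1, and on the more natural reading of 9.1.2, a patient whose steroid-requiring edema is first confirmed on the one-month MRI is scored a success in the test that decides whether glyburide goes forward. Starts on the day of the scan are undefined.

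The number of patients affected cannot be derived from the documents. If f is equal in both arms and the planned rates count these patients as failures, power drops to 0.76 at f = 0.1 and to 0.50 at f = 0.5. A reader might take the loss of power as established. It is not: only the scoring gap follows from the text. The stated power of 0.80 is itself correct for the inputs given.

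**What to change.** 1. In 9.1.2, 2.3.2 and 8.2.1, state that a corticosteroid for cerebral edema started at the one-month visit or MRI, or as a result of findings there, counts as a treatment failure. This also settles same-day starts. Attribution can use the start date and reason already collected under 4.2.7.3 and 4.2.8.2.
2. Reconcile 8.4.6 with 9.1.2, and with 2.1.2 and 2.3.2, so that one primary endpoint is stated and is the one tested in 9.3.2.
3. Optionally, add a sensitivity analysis with a failure window that ends on day 40 for everyone. It is less suitable as the main rule: study drug stops on the evening of the scan, so a patient scanned on day 25 would contribute 40 − 25 = 15 days off drug.

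The cost is wording in the protocol and analysis plan, agreed before unblinding. No new data are needed, and the conditions under which a steroid may be given do not change. The attribution rule does need a judgment on whether a start resulted from the one-month findings; that judgment should be made blinded, from the recorded reason.

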8.3 Imaging

- 8.3.1** All patients must have a contrast enhanced MRI within 60 days of study entry.
- 8.3.2** Pre-treatment tumor/edema ratio should be determined by importing the pretreatment MRI into the Eclipse treatment planning system. MRI with and without contrast.T1-weighted, T2 and/or FLAIR MRI of the brain (maximum slice thickness 5mm). FLAIR imaging is preferred. The total volume of tumor and total volume of edema should be recorded. If the ratio of edema/tumor volume is $\geq 35:1$, this will be counted as a risk factor for entering the trial on the Randomized Portion.
- 8.3.3** MRI obtained at the time of SRS (for treatment planning; may be within 21 prior to SRS treatment for patients being treated with linac-based radiosurgery where it is not standard of care to complete a MRI on the day of SRS [as it is with gamma knife]), at the time of the one month follow-up visit, and at the time of the 3 month follow-up visit must be taken with a MRI machine. These studies must all employ MRI with and without contrast. T1-weighted, T2 and/or FLAIR MRI of the brain (maximum slice thickness 5mm). FLAIR imaging is preferred.
- 8.3.4** FLAIR sequences at time of SRS (see note above regarding linac-based radiosurgery patients), one month follow-up, and 3 month follow-up MRI scans will be imported into the Eclipse treatment planning system where FLAIR volume will be automatically calculated using "Region Growing" on Eclipse (Appendix I). The automated contours will be verified and modified as needed by the radiation oncologist. Physicians, patients, and the study team will be blinded to the patient's investigational medication on the Randomized Portion. The primary endpoint of the Randomized Portion will constitute a mean of the edema values as measured by the region growing tool and verified and modified as needed by the radiation oncologist (see Appendix I).

8.3.5 T1 post gadolinium sequences at time of SRS (see note above regarding linac-based radiosurgery patients), one month follow-up, and 3 month follow-up MRI scans will be imported into the Eclipse treatment planning system where the enhancing tumor(s) that was treated with the full dose of SRS will be manually contoured by the radiation oncologist who will be blinded to patient's investigational medication on the Randomized Portion.

8.4 Definition of Edema Volume

- 8.4.1** Absolute edema volume will be calculated by subtracting the tumor volume as contoured on the T1 post gadolinium sequences (see Section 8.3.5) from the FLAIR edema volume (see Section 8.3.4).
- 8.4.2** Absolute edema will be independently verified and modified as needed by the radiation oncologist.
- 8.4.3** Absolute edema ≤ 1.00 cc will not be considered edema (defined as no edema).
- 8.4.4** Patients will be considered to have edema increase if an absolute edema increase is $\geq 5.0\%$ (this is an absolute percentage) from the time of SRS (see note above regarding linac-based radiosurgery patients) to the time of the one month follow-up MRI.
- 8.4.5** Patients with no edema at time of SRS (see note above regarding linac-based radiosurgery patients) who achieve an absolute edema value of > 1.00 cc at the time of the one month follow-up MRI will be considered to have an edema increase.
- 8.4.6** Primary endpoint of the Randomized Portion is edema increase as defined in Sections 8.4.4 and 8.4.5.

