APPENDIX I
"REGION GROWING" INSTRUCTIONS FOR ECLIPSE

- 1) After import MRI images into Eclipse, go to "**Contouring**", select the MRI image which you will use to contour, and double click. This should bring the selected image thumbnail to the top left portion of the screen.

Right Click on the image at the top left of the screen and select new structure. Under Label, type "Control Region". Under ID, type the name (example Edema_Pretx) and press "Create".

- 2) On the right taskbar, select "Imaging Threshold" and type in a range to encompass the hyperintense edema (Example Range 1000-2500). Click "Select VOI" and make the box encompass the area of edema at risk. Click Apply. If the range is not accurate, it may be modified.
- 3) This will create an ROI for edema that should then be modified by the physician to take out unnecessarily contoured structures (i.e. bone, calcifications, areas that are not consistent with edema. Edema should not include the appreciable gross tumor volume.
- 4) Select "Post Processing" and press "Apply to remove very small contoured areas.
- 5) Right click on the ROI at the top left and click "properties" to view and record the volume in cc's.

Separate ROIs maybe created for the gross tumor volume which should be manually contoured.

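### Appendix I step 3 and section 8.4.1 both take tumor out of the same FLAIR volume, so tumor shrinkage after SRS can be scored as an edema increase and tumor growth can hide one

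*Combined protocol and SAP*

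**What the plan says.** Four provisions together produce the edema volume.

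- Section 8.3.4 imports the FLAIR series into the planning system, "where FLAIR volume will be automatically calculated using" the region-growing tool, and refers to Appendix I for the method.
- Appendix I step 2 selects tissue by signal intensity. Step 3 has the physician edit the result and adds: "Edema should not include the appreciable gross tumor volume". Only at step 5 does the user open the contour's properties "to view and record the volume in cc's".
- Section 8.3.5 produces a separate tumor volume from the T1 post-gadolinium series, "where the enhancing tumor(s) that was treated with the full dose of SRS will be manually contoured by the radiation oncologist".
- Section 8.4.1 combines the two: "Absolute edema volume will be calculated by subtracting the tumor volume as contoured on the T1 post gadolinium sequences" from the FLAIR edema volume of 8.3.4.

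The result feeds three rules. Under 8.4.3, 1.00 cc or less is no edema. Under 8.4.4, a rise of at least 5.0% from SRS to the one-month MRI is an increase. Under 8.4.5, patients without edema at SRS "who achieve an absolute edema value of > 1.00 cc at the time of the one month follow-up MRI" also count as an increase. Section 8.4.6 then says: "Primary endpoint of the Randomized Portion is edema increase as defined in Sections 8.4.4 and 8.4.5".

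**The concern.** The 8.4.1 subtraction is applied to a contour from which tumor has already been edited out. Nothing in the plan says to skip it once step 3 has been done. Section 8.4.2 lets the radiation oncologist check and adjust the edema value but gives no rule about tumor.

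The second subtraction makes the edema measure depend on tumor size, and tumor size is expected to change after radiosurgery: 2.4.1.5 and 2.4.2.5 measure that change as an endpoint. A patient whose tumor responds well can be recorded as having worsening edema, and a patient whose tumor grows can have a real increase cancelled.

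At stake is the classification that 8.4.6 calls the randomized primary endpoint. Edema increase also appears in the primary objective (2.1.2) and primary endpoint (2.3.2). The FLAIR edema endpoints in 2.4.1.4 and 2.4.2.4 are affected too if they use the 8.4.1 volume, which they do not say. Equal error in the two arms cannot be assumed if glyburide works, because whether a patient is misclassified depends on edema volume and edema change.

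**Working it through.** **Plan's own figure.** The plan gives no number for this point. Its power figure of 0.80 (20 per arm, 50% against 75% success, one-sided 0.30) reproduces as 0.802 by full enumeration of Fisher's exact test. It is not affected by what follows.

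**Notation.** E is true tumor-free edema, T the T1 tumor volume, and r = E/T at SRS. The share of T already absent from the recorded FLAIR contour is f, taken to be the same at both scans. The documents do not fix f: step 3 speaks of *appreciable* tumor, while 8.3.5 contours enhancing tumor treated at full dose.

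- Recorded contour (Appendix I, step 5): E + (1 − f)T
- After 8.4.1: E + (1 − f)T − T = E − fT

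The value equals E only if f = 0, that is, only if step 3 removed no tumor.

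**False increase, 5% rule (8.4.4).** I read the 5% as relative to edema at SRS. Hold E constant and let the tumor shrink by fraction s. The reported change is fsT/(E − fT) = fs/(r − f). This is at least 0.05 when f < r ≤ f(1 + 20s), provided E − fT at SRS exceeds 1.00 cc. The largest r at which stable edema is scored as an increase is:

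| f | s = 10% | s = 25% | s = 50% | s = 100% |
|---|---|---|---|---|
| 1 | 3 | 6 | 11 | 21 |
| 0.75 | 2.25 | 4.5 | 8.25 | 15.75 |
| 0.5 | 1.5 | 3 | 5.5 | 10.5 |

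This route therefore stops at 21:1.

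**Examples at f = 1** (assumed volumes in cc; the documents give no patient volumes):

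| E | T | Reported E − T | True change | Scored |
|---|---|---|---|---|
| 20 to 20 | 5 to 3.5 | 15 to 16.5 (+10%) | 0% | increase (false) |
| 20 to 20 | 2 to 1 | 18 to 19 (+5.6%) | 0% | increase (false) |
| 15 to 13.5 | 5 to 2.5 | 10 to 11 (+10%) | −10% | increase (false) |
| 20 to 22 | 5 to 7 | 15 to 15 (0%) | +10% | no increase (missed) |
| 20 to 18.5 | 5 to 3.5 | 15 to 15 (0%) | −7.5% | no increase (correct) |
| 24 to 24 | 2 to 1 | 22 to 23 (+4.5%) | 0% | no increase (correct) |
| 105 to 105 | 3 to 0 | 102 to 105 (+2.9%) | 0% | no increase (correct) |

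Rows 1 and 5 have the same tumor change but different edema change, and only row 1 is misclassified. Partial exclusion weakens the effect: at f = 0.5, row 1 becomes 17.5 to 18.25, or +4.3%, and is not scored.

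**False increase, 1.00 cc rule (8.4.5).** This needs E − fT to be at most 1.00 cc at SRS and above it at one month. With E constant at 4 cc and T falling from 3.2 to 2.5 cc, the value goes from 0.8 to 1.5 cc. There is no ratio cap: with E 1.02 cc and T 0.03 to 0.01 cc (34:1), it goes from 0.99 to 1.01 cc.

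**Hidden increase.** If edema truly rises 10% and the tumor grows by fraction t, the reported change is (0.10r − ft)/(r − f). It falls below 5% when t > [0.10r − 0.05(r − f)]/f. At r = 2, 5 and 10 this is 15%, 30% and 55% for f = 1, and 25%, 55% and 105% for f = 0.5.

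**The case against.** The best defense is that step 3 and 8.4.1 describe a single operation. Step 3 states the aim, and the separate tumor contour that Appendix I allows, together with 8.4.1, carries it out. If 8.4.1 meant removing a region rather than a number of cc, a contour already free of tumor would lose nothing more. That reading is possible but less natural: step 5 records a cc figure, and 8.4.1 describes a calculation on two volumes obtained from different sequences. The plan never says the two steps are the same.

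Several further points stand and limit the size.

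- Section 9.1.2, the outcome tested under 9.3.2, defines failure by corticosteroid initiation or drug-related death, so these volumes do not enter it. The conflict between 9.1.2 and 8.4.6 is a separate matter.
- Readers are blinded in the randomized portion. If glyburide alters neither edema nor tumor, misclassification is expected to be equal between arms, so no inflation of false positives is shown. Blinding does not correct the arithmetic, however.
- An impossible result, such as E 6 cc with T 8 to 4 cc giving −2 to +2 cc, should be caught under 8.4.2. The plausible-looking errors above would not stand out.
- The 34:1 example involves tumors smaller than the permitted 5 mm slice. It shows only that no cap exists.
- A ratio of 35:1 or more at SRS protects against false increases under 8.4.4. In 3.1.9.1, though, it is one of four risk factors of which two suffice, and it is taken from an earlier MRI. The pilot requires none of them (3.1.10).

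**Conclusion.** The concern holds. Read in sequence, 8.3.4, Appendix I, 8.3.5 and 8.4.1 remove tumor twice, and no provision corrects it. The edema value becomes E − fT, so tumor change contaminates the 8.4.3 to 8.4.5 classification in both directions. With full exclusion, stable edema is scored as increased at ratios up to 3:1 for 10% tumor shrinkage, 11:1 for 50% and 21:1 for complete disappearance.

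These bounds rest on three assumptions: the 5% is relative to edema at SRS (8.4.4 calls it an absolute percentage without explaining that), f is the same at both scans, and true edema is constant. The plan gives no distribution of f, of tumor shrinkage or of ratios, so no count of affected patients can be derived. Because the 9.1.2 outcome is untouched, this should be fixed before any edema volume is analyzed, but it does not undermine the planned primary test.

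**What to change.** Remove tumor exactly once, by the same rule at every scan. Either option works.

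- **(a) Drop the subtraction.** Reword 8.4.1 so that absolute edema is the volume of the Appendix I contour, from which tumor has been excluded, with no further subtraction. State in step 3 which tumor contour defines the exclusion. This departs from the subtraction used in the historical series (section 1.8), and any tumor not excluded on FLAIR stays in the edema volume.
- **(b) Keep the subtraction.** Change Appendix I step 3 so that the FLAIR contour includes the tumor, adding any part that the step 2 intensity range missed. This matches the historical definition, but contours with tumor already edited out must be corrected.

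Use the same edema volume for the entry ratio in 8.3.2, which says "The total volume of tumor and total volume of edema should be recorded" without giving the rule. At f = 1, with T = 1 cc, a second subtraction turns 35:1 into 34:1. A contour that includes tumor, with no subtraction, turns 34:1 into 35:1. Also state whether 2.4.1.4 and 2.4.2.4 use this volume.

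The text change is one sentence in 8.4.1 or step 3, plus a cross-reference in 8.3.2 and a line on the secondary endpoints. The real work is checking stored contours against the chosen rule before recomputing volumes. Sample size, alpha and power do not change.
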